Study Design Overview: We propose to study the separate and combined effects of the FDA-approved cannabinoid dronabinol (Marinol) and the prototypical opioid hydromorphone (Dilaudid). Following telephone and screening to establish study eligibility, a cohort of **n=100** adults with knee osteoarthritis (KOA) will complete four different within-subject experimental sessions. Participants will complete one of two Phases, receiving either a 4mg or 2mg dose of hydromorphone. Randomization will be split equally across the two Phases. During each session, participants will complete baseline QST, questionnaires, and a neurocognitive battery. Oral hydromorphone will be administered in the first session. Subsequent sessions will consist of 1 of 3 conditions, and session order will be randomized and counter-balanced. Conditions will be 1) placebo; 2) oral dronabinol (10mg); and 3) combined hydromorphone and dronabinol (10mg). Measures will be repeated throughout the session to fully characterize the drug effects. Participants and staff will be kept blinded to the study medications under investigation, and participants will be informed in the consent form they may receive a combination of FDA-approved stimulants, benzodiazepines, opioids, cannabinoids, over-the-counter medications or placebo, though the participants will not actually be receiving stimulants, benzodiazepines, or over-the-counter drugs. All participants will be provided with transportation to and from the experimental sessions. Primary outcomes are measures of clinical pain, central sensitization, physical function and drug effects/adverse events. A subset of participants will undergo blood draws for pharmacokinetic (pK) profile. This will be voluntary and should aid recruitment as those that do not want an IV will still be allowed to participate in the study. We will aim to recruit 30 participants that volunteer to undergo IV/blood drawing procedures in order to characterize pK.

Phase 1: The initial Phase of this project will include hydromorphone at a dose of 4mg.

Phase 2: The second Phase of this project will include hydromorphone at a dose of 2mg in order to evaluate drug effects at a reduced opioid dose.

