Hydromorphone: Hydromorphone hydrochloride is a pure mu opioid agonist that can be administered in oral, rectal, intramuscular (IM) or intravenous (IV) formulations for the indication of acute and/or chronic pain. We have chosen to administer hydromorphone because we have extensive experience administering hydromorphone in all formulations^{96; 109-117}, and know that it will produce reliable and consistent results that will aid interpretation of outcomes. Hydromorphone was also selected as the exemplar opioid for this study because it is not subject to differences in CYP metabolic enzymes and therefore will not require us to screen out individuals with recent exposure to CYP inhibiting or inducing medications, or to analyze and statistically control for CYP metabolic profiles in individual subjects. There is also no apparent effect of gender on the pharmacokinetics of hydromorphone. We have selected a low and mid-level dose because they are within the range of doses approved by the FDA. They are also sensitive to the QST tests we have proposed, and we therefore believe both will provide an ideal opportunity to evaluate whether the curve of hydromorphone is shifted as a function of dronabinol administration.

Dronabinol: Dronabinol is a schedule II drug that is being administered at 10 mg, which is consistent with the range approved by the FDA for therapeutic use in patients with chemotherapy-induced nausea and vomiting, and loss of appetite in patients with advanced HIV (AIDS). Dronabinol is also used off label for the treatment of Gilles de la Tourett's syndrome, general loss of appetite (related to cancer), spasticity from Multiple Sclerosis, treatment refractory and postoperative nausea and vomiting, and treatment refractory pruritus. When administered orally (as proposed here), dronabinol reaches peak concentrations in 2-4 hours and is 10-20% bioavailable. It is subject to extensive first-pass metabolism and is excreted in fecal (35-50%) and renal (10-15%) waste, with an elimination half-life of 19-36 hours.

We have selected oral dronabinol because it is FDA approved for pain conditions and more likely than nabilone to be prescribed in practice due to cost. We believe this approach will yield data that can be instantly utilized by pain treatment specialists, which increases the generalizability of our study approach.

c. Justification and safety information if non-FDA approved drugs without an IND will be administered.

N/A

7. Study Statistics

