- Aim 4: Evaluate the pharmacokinetic (pK) and pharmacodynamic (pD) profile of the cannabinoid, opioid, and the combination in OA patients.** Hyp 7 (pK) will be assessed by evaluating Cmax (maximum concentration) and Tmax (time to maximum concentration) as a function of Drug condition using 1-factor models. We will also examine linear and quadratic effects to evaluate the time course of concentration. Linear and quadratic effects will be modeled for Hyp8 (pD) and analyzed by evaluating VAS and physiological ratings, transformed to change from baseline, evaluating area under the curve and peak change from baseline to identify main effects of the Drug condition. We will then conduct multivariate regression analyses to evaluate the degree to which the Cmax and Tmax correlate with pharmacodynamic outcomes, including abuse liability ratings, VAS ratings of drug effects, and cognitive testing outcomes.

Statistical analyses will be conducted separately by Phase and use multilevel analyses with an autoregressive (AR1) or compound symmetry (CS) covariance structures (as appropriate for the data set) using SAS PROC MIXED¹³⁷. Interpretation of drug condition main effects and interactions will rely on Tukey post-hoc tests. Statistical significance will be set at $p < 0.05$.

Expected Outcomes: We expect that dronabinol will enhance hydromorphone-induced analgesia to both clinical and laboratory-evoked pain. Our comprehensive battery of rigorous, testing procedures provides an opportunity to test effects on multiple mechanisms of experimentally-induced pain. We also expect improvement in physical functioning under combined dosing, and that the addition of the cannabinoid will not significantly increase the overall abuse liability or adverse event profile. We do suspect the cannabinoid may have cognitive effects (though the degree to which this may happen is not clear).

b. Secondary outcome variables.

Demographic and drug use characteristics that are hypothesized a priori to be associated with outcomes (e.g., Body Mass Index) will be compared across sex groups and significant differences will be included as covariates in the subsequent analyses. All analyses will be repeated and sex (male/female) will be added as a factor to the analyses.

c. Statistical plan including sample size justification and interim data analysis.

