This will be the first study to examine interactions between cannabinoids and opioids on clinical and laboratory-evoked measures of pain in a population who has chronic pain and central sensitization. The study uses a within-subject, placebo-controlled design and no data exist upon which to generate a power analysis. We have selected two primary outcomes for the measurement of analgesia: measures of conditioned pain modulation and time to hand withdraw latency in a cold presser test.

[name], a biostatistician with extensive experience analyzing within-subject laboratory tests of drug effects, conducted a revised power calculation based on new literature that employs methods similar to those of this study (Cooper et al., 2018). Sample size estimates were premised with a power of 0.8, alpha =0.05 and calculated effect sizes (Cohen, 1988). These analyses suggests a sample size ranging from 10-15 individuals would be sufficient to detect large effect sizes. Because one of our aims focuses on a sex-comparison, we originally planned to double our enrollment. Thus, our sample of 64 completers (32/sex) will yield sufficient power to evaluate direct effects of study condition on CPM and cold presser in both Phases, even at small effect size levels, and will also be sufficient to identify between-session differences on pK results¹⁴⁰.

d. Early stopping rules.

The safety of participants is the highest priority. The largest potential risk of this study is cardiovascular in nature. This notion is based upon the results of a published study that reported an increase in heart rate and blood pressure among patients exposed to the cannabinoid dronabinol who were also undergoing opioid withdrawal (of which increased heart rate and blood pressure is a known symptom). This group differs from our target population in many ways, however out of an abundance of caution in these early studies, we will use this experience to inform our safety criteria. We will monitor vital signs at all study data collection time points and will follow procedures that we have developed and successfully used in previous studies that administered drugs (e.g., cocaine) with known cardiovascular risks. Specifically, if a participant's parameters reach these thresholds, then a study physician, who will always be available via telephone, will be contacted and consulted to determine the appropriate course of action.

- Systolic blood pressure: $\geq 180\text{mm Hg}$

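### Analysing the Phases only separately halves the data for dronabinol versus placebo, a contrast that both Phases share, and leaves dronabinol's added effect at 2 mg and at 4 mg uncompared

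*Combined protocol and SAP*

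**What the plan says.** Section 4a (Study Design Overview) has two Phases: "Participants will complete one of two Phases, receiving either a 4mg or 2mg dose of hydromorphone". It adds "Randomization will be split equally across the two Phases", but also calls the 4 mg Phase the initial one and the 2 mg Phase the second. Phase 2 is included "in order to evaluate drug effects at a reduced opioid dose".

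Tables 1a and 1b differ only in the hydromorphone dose of conditions 1 and 4. Condition 2 (double placebo) and condition 3 (dronabinol 10 mg with hydromorphone placebo) are the same in both. Hydromorphone alone is always the first session; the other three conditions follow in randomised, counterbalanced order.

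Section 6b says that the two doses allow the team to "evaluate whether the curve of hydromorphone is shifted as a function of dronabinol administration". The dose rationale earlier in section 6 says that having both helps to tell an additive from a synergistic or absent effect.

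Section 7a then specifies: "Statistical analyses will be conducted separately by Phase". Its models contain Drug and Time, with session number or sex in places. No Phase term, hydromorphone-dose term or pooled analysis appears in section 7. Section 7c says that "our sample of 64 completers (32/sex) will yield sufficient power to evaluate direct effects of study condition" in both Phases.

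**The concern.** Two things are lost when nothing is estimated across Phases.

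First, dronabinol alone versus placebo uses the same two treatments in both Phases, within person and in randomised order. Splitting it gives two estimates, each with a standard error about 1.4 times that of a combined one.

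Second, each participant takes only one active hydromorphone dose, so dronabinol's added effect at 2 mg and at 4 mg can be compared only across Phases. With no such contrast planned, a reader who wants to know whether the effect depends on dose has only two sets of p-values to set side by side. One significant and one non-significant result is not evidence of a difference, and here that pattern would often arise by chance.

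**Working it through.** **Inputs from the documents.** 100 enrolled, split equally, so 50 per Phase (section 4a). 64 completers, alpha 0.05, power 0.80 (section 7c). Tukey tests over four conditions (section 7a).

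**Assumptions.** The 64 is the total, about 32 per Phase; 64 in each Phase would need 128 people, more than the 100 enrolled. Tests are two-sided. Effects are in SD units of the within-person difference. The documents give no numerical effect size, so 0.2, 0.35 and 0.5 are shown.

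**The plan's own figure.** Section 7c gives 10 to 15 people for large effects. With a paired standardised difference of 0.8, n = 15 (two-sided t), 13 (two-sided normal), 12 (one-sided t) or 10 (one-sided normal). The range reproduces on that assumed benchmark.

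**Dronabinol versus placebo, unadjusted.** The detectable difference is about (1.960 + 0.842)/√n, which is 0.50 for n = 32 and 0.35 for n = 64. The exact noncentral t, with noncentrality d√n and n − 1 degrees of freedom, gives:

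| n | Detectable at 80% power | Power at 0.2 SD | Power at 0.35 SD | Power at 0.5 SD |
|---|---|---|---|---|
| 32 (one Phase) | 0.51 | 20% | 48% | 78% |
| 64 (pooled) | 0.36 | 35% | 79% | 98% |
| 50 (one Phase, all complete) | 0.40 | 28% | 68% | 93% |
| 100 (pooled, all complete) | 0.28 | 51% | 93% | 99.9% |

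The standard error ratio, pooled to single Phase, is √(32/64) = 0.71. Keeping a Phase-by-condition term costs almost nothing here: the equally weighted mean of two Phase estimates has variance (σ²/32 + σ²/32)/4 = σ²/64.

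**With Tukey over four conditions.** Assume sphericity and 3(n − 1) error degrees of freedom. The critical t is q/√2: 3.70/√2 = 2.62 for n = 32 and 3.67/√2 = 2.59 for n = 64. At 0.35 SD the noncentralities are 0.35 × √32 = 1.98 and 0.35 × √64 = 2.80, giving power of about 27% and 58%.

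**Chance of discordant Phases.** If the true effect is 0.35 SD in both, the probability that exactly one unadjusted test is significant is 2 × 0.48 × 0.52 = 0.50.

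**Which cross-Phase contrast is clean.** Let δ₂ and δ₄ be dronabinol's added effect on top of 2 mg and 4 mg, δ₀ its effect on top of placebo, s₁ the session-1 effect and s̄ the mean effect of sessions 2 to 4.

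- Combination minus hydromorphone alone estimates δ + s̄ − s₁ in each Phase. The difference between Phases is δ₄ − δ₂: order cancels if it is equal in both Phases.
- (Combination minus hydromorphone alone) minus (dronabinol minus placebo) estimates δ − δ₀ + s̄ − s₁. Order does not cancel, so an interaction that uses the 0 mg cells is confounded with session 1.
- If the dose response is linear and dronabinol moves it sideways, y = a + b(dose + k), the added effect is bk at every dose. Then δ₄ − δ₂ = 0 although the curve has shifted.

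**Precision of δ₄ − δ₂.** It is a two-group comparison of within-person contrasts: (1.960 + 0.842) × √(2/n) = 0.70 SD with 32 per Phase and 0.56 SD with 50. The exact t raises the first to about 0.71. Power at 0.5 SD is about 52% and 71%.

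**The case against.** The strongest reply is that separate analysis is a legitimate choice. The combination and hydromorphone-alone conditions contain a different dose in each Phase, so Phase-specific estimates are right for the main contrasts. This stands, and those results should be kept.

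A reader might infer that Phase 2 cannot serve its purpose. The documents do not support that: section 4a states the purpose as studying drug effects at a lower dose, and a separate Phase 2 analysis does so. Nor is the curve shift a promised hypothesis. It appears in the dose justification of section 6b and is not one of Hyp1 to Hyp8. Additivity at a single dose could also be examined inside one Phase, which holds all four cells of a 2 × 2, although no such contrast is written.

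It is equally tempting to call a 0/2/4 mg dose-by-dronabinol interaction the test of a shifted curve. It is not: a parallel shift leaves it at zero, and the 0 mg cells bring in the fixed first session.

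Finally, the dronabinol-versus-placebo contrast cannot simply be declared free of Phase. Section 8b uses session 1 to exclude people with untoward effects of the hydromorphone dose they received, so those who reach the later sessions may be selected differently in each Phase. That calls for a heterogeneity check; it does not rule out pooling. The plan also nowhere proposes to compare significance between Phases; that risk lies in how readers use the results.

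**Conclusion.** The point holds as a gap in what is estimated; it does not make the separate analyses wrong. For dronabinol versus placebo, the plan accepts a detectable difference of 0.51 SD where 0.36 SD is available from the same data. This rests on 64 being the total, an even split and unadjusted paired tests. Under Tukey absolute power is lower, but the loss remains. Pooling does not rescue small effects: power at 0.2 SD is only 35% with 64 people.

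The dependence of dronabinol's added effect on hydromorphone dose is not estimated at all, although the two-dose rationale invites it. Any such estimate will be imprecise, and it is a randomised comparison only if participants are allocated to Phases at random and concurrently, which section 4a leaves unclear.

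**What to change.** Keep the by-Phase analyses. Add to section 7 one pooled secondary mixed model with fixed effects for condition, time, Phase, Phase-by-condition and session number, and random effects for participant and session. Enter session number as a class variable and note that session 1 coincides with hydromorphone alone, so its effect cannot be separated from that condition. Prespecify two contrasts:

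1. Dronabinol alone versus placebo, averaged over Phases, with the Phase-by-contrast term reported as a heterogeneity check. Report that term with its interval, since with about 32 per Phase it too detects only about 0.7 SD.
2. The difference between Phases in combination minus hydromorphone alone, with a confidence interval. Describe it as asking whether dronabinol's added effect depends on hydromorphone dose, and not as a test of a curve shift. State that it is between participants, has limited precision, and assumes an equal session-1 effect in both Phases.

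Do not use a 0/2/4 mg interaction that relies on the 0 mg cells. State in section 4a whether allocation to Phase is randomised or sequential; if sequential, label contrast 2 non-randomised. Align the curve-shift wording in section 6b with what contrast 2 can show.

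The cost is some SAP text and one extra model, with no new data. The drawback is the low precision of contrast 2.

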This laboratory study will evaluate whether a cannabinoid enhances the analgesic efficacy of an opioid in a clinical sample of chronic pain patients, laying the foundation for a larger clinical trial evaluating the utility of cannabinoids as potentially opioid-sparing adjuvants to chronic opioid therapy for pain. Heightened CNS processing, or central sensitization (CS), occurs across numerous chronic pain conditions and is an important treatment target in its own right. While cannabinoids show initial promise as treatments or adjuncts for some chronic pain conditions and pre-clinical data suggest effects on CS, little is known about the degree to which combining cannabinoids with opioids alleviates CS-mediated chronic pain. We propose a within-subject, single exposure, double-blind, placebo-controlled, human laboratory investigation of the extent to which a cannabinoid enhances opioid analgesia in a model chronic pain population (e.g., patients with knee osteoarthritis). Human laboratory studies are an ideal method for this initial evaluation because they provide the opportunity to tightly control study drug dosing and afford high sensitivity of measurements, and enable tight control of confounding variables that may otherwise exist in clinical treatment populations and could differentially impact outcomes. This approach will minimize the number of participants needed to determine whether a positive signal exists while permitting rigorous and elegant evaluation of the study aims. Primary study outcomes will include measures of clinical pain and central sensitization, physical function, drug effects (e.g., abuse liability, adverse events, cognitive performance), and pharmacokinetic analyses. The Aims will examine the magnitude and duration of cannabinoid/opioid combination in reducing clinical pain and central sensitization; the effects on physical functioning, adverse events and indices of abuse liability; and the pharmacokinetic and pharmacodynamics profiles for the individual and combined drugs. This study will provide the most systematic and rigorous evaluation of the potential for cannabinoids to enhance analgesic effects of opioids in human subjects to date, and will do so in a relevant and generalizable clinical pain population who has CS, which makes these results more directly relevant compared to studies conducted in healthy populations. These findings will be critical to informing the efficacy and safety profile for the advancement of opioid/cannabinoid combination regimens to clinical trials with chronic pain patients.

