a. Primary outcome variable:

Aim 1: Evaluate the magnitude and duration of cannabinoid/opioid combination to reduce clinical pain (Hyp1) and central sensitization (Hyp2). Hyp1 (pain VAS) and Hyp 2 (CS) will be analyzed using repeated 2-factor (Drug x Time) models that examine linear and quadratic effects as well as duration and magnitude, and direct and interaction effects. If large variation exists across subjects at baseline, then raw data will be transformed to change-from-baseline and analyzed in drug condition by time models. A secondary outcome will be peak change from baseline, analyzed as a function of Drug (1-factor model).

- Aim 2: Evaluate the degree to which physical functioning is altered by the cannabinoid/opioid combination.** Hyp3 will be assessed using the TUG and 6MWT. Time to complete the TUG task will be the primary outcome and will be evaluated using 2-factor (Drug x Time: Pre to Peak) models.
- Aim 3: Conduct a direct comparison of the subjective, physiological, abuse liability, and cognitive effects of the cannabinoid, opioid, and combination.** Hyp4 (adverse events) will be assessed by summing the mean number of related mild, moderate, and severe adverse events (separately) and using 1 factor models to assess a main effect of Drug. Hyp5 (abuse liability) will be assessed using the Drug vs. Money questionnaire and changes in VAS ratings using 2-factor models (Drug x Time). Hyp6 will evaluate changes in neurocognitive performance, including study session number as a covariate to control for practice effects, using 2-factor (Drug x Time) analyses. Secondary outcomes for this hypothesis will be analysis of peak change from baseline for the cognitive outcomes, analyzed using 1-factor (Drug) ANOVAs to evaluate a main effect of drug.

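### Sections 7.a, 4.a and 7.c name different sets of primary outcomes, each tested at 0.05 in two separate Phases with no ranking, so no single result is fixed in advance as the trial's primary finding

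*Combined protocol and SAP*

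**What the plan says.** - Section 7.a, headed "a. Primary outcome variable", covers all four aims and Hyp1 to Hyp8. Only the peak-change analyses (Aim 1 and the cognitive outcomes) are called secondary there. Time on the Timed Up and Go (TUG) is named primary for Aim 2.
- Section 7.b, meant for secondary outcomes, names no secondary endpoint. It describes covariates and a repeat of every analysis with sex as a factor.
- Section 4.a, Study Design Overview: "Primary outcomes are measures of clinical pain, central sensitization, physical function and drug effects/adverse events".
- The Section 1 abstract is broader and closes its list with drug-level analyses: "Primary study outcomes will include measures of clinical pain and central sensitization, physical function, drug effects (e.g., abuse liability, adverse events, cognitive performance), and pharmacokinetic".
- Section 7.c says that two primary outcomes for analgesia were chosen: CPM and cold pressor withdrawal latency. Under Aim 1, 7.a analyses pain VAS and the central sensitization (CS) index instead.
- For Aim 1, the models are "repeated 2-factor (Drug x Time) models that examine linear and quadratic effects as well as duration and magnitude, and direct and interaction effects".
- On the Phases and the model, 7.a states: "Statistical analyses will be conducted separately by Phase and use multilevel analyses with an autoregressive (AR1) or compound symmetry (CS) covariance structures". The threshold is 0.05. Drug main effects and interactions are read through Tukey post-hoc tests.

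**The concern.** Tukey limits error among drug pairs inside one model. It does nothing across endpoints, across several terms of the same model, or across the two Phases. With three differing statements of what is primary and no order among them, a significant result on any of several outcomes, in either Phase, could be reported as a primary finding, and a positive Phase could be put ahead of a negative one. Section 1 says the results will inform whether combination regimens advance to clinical trials, so it matters which result was to carry that weight.

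**Working it through.** **Inputs from the documents.** Threshold 0.05 per test (7.a; sidedness not stated, two-sided assumed). Four conditions (Tables 1a and 1b). The Phases use different people (4.a: "Participants will complete one of two Phases, receiving either a 4mg or 2mg dose of hydromorphone"), so their errors are independent.

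**Assumptions.** One test per endpoint. Endpoint correlation from 0 to 0.9, as the documents give none. 32 completers per Phase: the 64 in 7.c halved (the 32 printed there is per sex).

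**1. The plan's own figure.** No family-wise rate is stated. The 10-15 participants in 7.c for a large effect reproduce at an unadjusted 0.05 and power 0.8. With a paired effect of 0.8, the exact t test needs 15 two-sided or 12 one-sided. A four-condition repeated-measures F test with f = 0.40 needs 14 or 10 at correlation 0.3 or 0.5. So the sample size makes no allowance for multiplicity.

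**2. Any significant Drug effect counts, and drug does nothing.** With p the error rate in one Phase, the rate over two Phases is 1 − (1 − p)². Under independence, k tests in all give 1 − 0.95^k.
- One endpoint, two Phases: 1 − 0.95² = 9.75%.
- The two outcomes in 7.c: 1 − 0.95⁴ = 18.5%. At correlation 0.9, p = 7.04% and 1 − 0.9296² = 13.6%.
- Hyp1 to Hyp3: 1 − 0.95⁶ = 26.5%. At correlation 0.5, p = 12.6% and 1 − 0.874² = 23.6%. At 0.8, p = 9.9% and 1 − 0.901² = 18.8%.

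**3. Combination versus hydromorphone alone, after Tukey on condition means.** With 3 × 31 = 93 error degrees of freedom and four means, the 5% studentized range point is 3.70. That is t = 3.70/√2 = 2.616, or two-sided p = 0.0104 per comparison. This null can hold even if hydromorphone works.

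| Endpoints, two Phases | Correlation 0 | 0.5 | 0.8 |
|---|---|---|---|
| Hyp1-3 | 1 − 0.9896⁶ = 6.1% | 1 − (1 − 0.0283)² = 5.6% | 1 − (1 − 0.0225)² = 4.5% |
| Eight | 1 − 0.9896¹⁶ = 15.4% | 1 − (1 − 0.0635)² = 12.3% | 1 − (1 − 0.0402)² = 7.9% |

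The one-Phase values in columns 0.5 and 0.8 come from simulating equicorrelated normal statistics at that threshold. Time, linear, quadratic and interaction terms are not counted and would add to these rates.

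**4. The strictest claim.** Suppose success means beating hydromorphone, dronabinol and placebo together. If hydromorphone works and dronabinol adds nothing, the false-claim rate is about half of 0.0104, or 0.5%, per endpoint per Phase. For Hyp1 to Hyp3 over two Phases, 1 − 0.995⁶ = 3.0%.

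**The case against.** The strongest reply is that step 2 counts the wrong event. Section 2 words Hyp1 to Hyp3 as the combination outperforming each drug alone and placebo, and Section 6 expects both hydromorphone doses to relieve pain, so an overall Drug effect on pain would not be a false finding. Read as a joint requirement, the error for Hyp1 to Hyp3 is about 3%, below 5%. This stands for condition means. But 7.a states no success rule, and the time-related terms lie outside the calculation.

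A reader might infer that eight primary hypotheses in two Phases give a false-finding rate of 25-56% (25% in one Phase at correlation 0.5, up to 1 − 0.95¹⁶ = 56% over two Phases if independent). The documents do not support that reading. Hyp4 and Hyp5 predict no increase, so rejecting their null does not yield the hypothesised finding. For Hyp7, peak concentration cannot be equal across conditions that include placebo. The eight-endpoint row in step 3 is therefore a count of false significant contrasts of any kind, not of false claims of benefit.

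It is also fair that the primary heading belongs to an IRB form, so placement under it is weak evidence of confirmatory intent, and that this is an early laboratory study with two doses analysed apart. Yet 1, 4.a and 7.c use the word primary in the sponsor's own prose, with different contents. Nor is 7.c a hierarchy that settles the matter, since its two outcomes are not the Aim 1 endpoints of 7.a.

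**Conclusion.** The concern holds as a failure to fix one primary result, with error inflation that is real on some readings and small on others. Over two Phases it is about 14-19% (7.c outcomes) or 19-26% (Hyp1 to Hyp3) if any Drug effect counts under a global null. For the contrast that answers the trial's question, it is about 6% for Hyp1 to Hyp3 and 12-15% over eight endpoints at correlations of 0.5 to 0, and lower at 0.8. It is about 3% if all three comparators must be beaten on Hyp1 to Hyp3. All of this rests on assumed correlations and one test per endpoint; the Tukey figures also assume 32 per Phase, though they hardly change with 50. The contradiction between 7.a, 4.a and 7.c rests on no assumption. The plan should be changed, but it does not support a claim that the error rate is many times 5% whatever is counted.

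**What to change.** 1. Make 7.a, 4.a, 7.c and the abstract name the same single primary endpoint. Pain VAS, the CS index, CPM and cold pressor latency are the candidates in the text. The choice is the sponsor's, made before unblinding. Changing 7.a alone would leave 7.c contradicting it.
2. Name one primary contrast, combination versus hydromorphone alone, and the model term or summary that tests it. If the joint rule against all three comparators is intended, state that.
3. Put any remaining efficacy endpoints in a fixed order within each Phase, stopping at the first non-significant result.
4. For a claim that holds if either Phase succeeds, apply Holm to the two Phase p-values of the primary endpoint (smaller below 0.025, other below 0.05). State whether alpha released by one Phase passes to the other Phase or down the order, since it cannot do both.
5. Label the other hypotheses and the linear and quadratic terms secondary or exploratory, with confidence intervals. Peak change already has that status for Aim 1 and cognition.

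This is wording only, with no new data. The costs are that endpoints lower in the order lose formal status if an earlier one fails, and that Holm lowers single-Phase power. For a paired t test at a standardised difference of 0.5 (assumed), power at 0.05 versus 0.025 falls from about 78% to 68% with 32 per Phase, or from 93% to 89% with 50 per Phase (all 100 enrolled, split equally, completing).
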